5.1.2 Retention

Once a participant is enrolled/randomized in MTN-024/IPM 031, the study site will make every effort to retain the participants in follow-up to minimize possible bias associated with loss-to-follow-up. An average retention rate of 95% will be targeted at each site. All study sites will be responsible for developing and implementing local standard operating procedure (SOPs) to achieve this. Engaging peer educators/advocates or organizations in retention messaging, etc. may be used to facilitate MTN-024/IPM 031 retention.

5.2 Inclusion Criteria

Females must meet all of the following criteria to be eligible for inclusion in the study:

- 1) Age 45 through 65 years (inclusive) at Screening, verified per site SOPs
- 2) Per participant report, postmenopausal at Screening, defined as amenorrheic for the past 12 months (minimum) or at least 6 months status post-bilateral oophorectomy
- 3) Follicle-stimulating hormone (FSH) level at 40 mIU/ml or higher at Screening

- 4) Able and willing to provide written informed consent to be screened for and enrolled in MTN-024/IPM 031
- 5) Able to communicate in spoken and written English
- 6) Able and willing to comply with all study procedural requirements
- 7) Willing to only use study provided and/or approved vaginal products throughout the duration of study participation.
- 8) Willing to abstain from inserting study approved lubricant into the vagina for 72 hours prior to each visit
- 9) Willing to abstain from vaginal intercourse for 72 hours prior to each visit
- 10) In general good health as determined by the Investigator of Record (IoR)/designee at Screening and Enrollment
- 11) Able and willing to provide adequate locator information, as defined in site SOPs
- 12) HIV-uninfected based on testing performed at Screening (per protocol algorithm in Appendix II)
- 13) Per participant report at Screening and Enrollment, agrees to use male latex condoms for sexual intercourse
- 14) Per participant report at Screening and Enrollment, states a willingness to refrain from inserting any non-study vaginal products or objects into the vagina including, but not limited to spermicides, female condoms, diaphragms, topical or systemic hormone replacement therapy, including vaginal estrogens, and/or hormonal contraceptives, vaginal medications, menstrual cups, cervical caps (or any other vaginal barrier method), vaginal douches, lubricants and moisturizers, sex toys (vibrators, dildos, etc.), for the duration of the study participation.

Note: Use of study approved lubricant is permitted.

- 15) At Screening and Enrollment, agrees not to participate in other research studies involving drugs, medical devices, vaginal products, or vaccines for the duration of study participation

Participants in the biopsy subset must also meet the following criteria at Screening to be eligible for inclusion:

- 16) Willing to abstain from inserting anything into the vagina for 72 hours following the collection of biopsies, including abstaining from vaginal intercourse

17) Anatomy sufficient for the collection of cervical biopsies

5.3 Exclusion Criteria

Females who meet any of the following criteria will be excluded from the study:

- 1) Per participant report at screening:
 - a) Plans to relocate away from the study site during study participation
 - b) Plans to travel away from the study site for more than 4 consecutive weeks during study participation

- 2) Pregnant at screening

Note: A documented negative pregnancy test performed by study staff is required for inclusion; however a self-reported pregnancy is adequate for exclusion from the study.

- 3) Diagnosed with urinary tract infection (UTI) at Screening or Enrollment

Note: Otherwise eligible participants diagnosed with UTI during screening are offered treatment and may be enrolled after completing treatment and all symptoms have resolved. If treatment is completed and symptoms have resolved within 45 days of obtaining informed consent for screening, the participant may be enrolled.

- 4) Diagnosed with pelvic inflammatory disease, an STI or reproductive tract infection (RTI) requiring treatment per current Centers for Disease Control and Prevention (CDC) guidelines at Screening or Enrollment

Note: Otherwise eligible participants diagnosed during screening with pelvic inflammatory disease or STI/RTI requiring treatment per CDC guidelines — other than asymptomatic bacterial vaginosis (BV) and asymptomatic candidiasis — are offered treatment and may be enrolled after completing treatment and all symptoms have resolved. If treatment is completed and symptoms have resolved within 45 days of obtaining informed consent for screening, the participant may be enrolled. Genital warts requiring treatment also must be treated prior to Enrollment. Genital warts requiring therapy are defined as those that cause undue burden or discomfort to the participant, including bulky size, unacceptable appearance, or physical discomfort.

- 5) Has a clinically apparent Grade 2 or higher pelvic exam finding (observed by study staff) at Screening or Enrollment, as per the Division of AIDS Table for Grading the Severity of Adult and Pediatric Adverse Events Version 1.0, December, 2004 (Clarification dated August 2009), Addendum 1-Female Genital Grading Table for Use in Microbicide Studies

Note: Cervical bleeding associated with speculum insertion and/or specimen collection judged to be within the range of normal according to the clinical judgment of the Investigator of Record (IoR)/designee is considered expected non-menstrual bleeding and is not exclusionary.

Note: Otherwise eligible participants with exclusionary pelvic exam findings may be enrolled/randomized after the findings have improved to a non-exclusionary severity grading or resolved. If improvement to a non-exclusionary grade or resolution is documented within 45 days of providing informed consent for screening, the participant may be enrolled.

- 6) Participant report and/or clinical evidence of any of the following:
 - a) Known adverse reaction to any of the study products (ever)
 - b) Known adverse reaction to latex (ever)
 - c) Chronic and/or recurrent vaginal candidiasis
 - d) Topical or systemic hormone replacement therapy and/or hormonal contraception within the 6 months prior to Enrollment
 - e) Non-therapeutic injection drug use in the 12 months prior to Enrollment
 - f) Post-exposure prophylaxis (PEP) for HIV exposure within the 6 months prior to Enrollment
 - g) Pre-exposure prophylaxis (PrEP) for HIV prevention within the 6 months prior to Enrollment
 - h) Last pregnancy outcome 6 months or less prior to Enrollment
 - i) Gynecologic or genital procedure (e.g., tubal ligation, dilation and curettage, piercing) 90 days or less prior to Enrollment
 - j) Currently breastfeeding
 - k) At Screening, severe pelvic relaxation such that either the vaginal walls or the uterine cervix descend beyond the vaginal introitus with valsalva maneuver
 - l) Participation in any other research study involving drugs, medical devices, vaginal products, or vaccines, in the 45 days prior to Enrollment
- 7) As determined by the IoR/designee, any significant uncontrolled active or chronic cardiovascular, renal, liver, hematologic, neurologic, gastrointestinal, psychiatric, endocrine, respiratory, immunologic disorder or infectious disease
- 8) Has any of the following laboratory abnormalities at Screening Visit:
 - a) Aspartate aminotransferase (AST) or alanine transaminase (ALT) Grade 1 or higher*
 - b) Creatinine Grade 2 or higher*
 - c) Hemoglobin Grade 2 or higher*
 - d) Platelet count Grade 1 or higher*
 - e) Pap result Grade 2 or higher**

Note: Otherwise eligible participants with an exclusionary test may be re-tested during the screening process.

Note: Women with a documented normal result within the 12 months prior to Enrollment need not have a Pap smear during the screening period. Women with a Grade 1 abnormal Pap smear can be enrolled upon completion of the initial phase of evaluation if no current treatment is indicated (based on local standard of care for management of abnormal cervical cytology). Need for a repeat Pap within 6 months does not preclude Enrollment prior to that result becoming available. If the participant has had a

hysterectomy for reasons not related to cervical dysplasia, a Pap smear need not be performed.

- 9) Has any other condition that, in the opinion of the IoR/designee, would preclude informed consent, make study participation unsafe, complicate the interpretation of study outcome data, or otherwise interfere with achieving the study objectives

*Division of AIDS Table for Grading the Severity of Adult and Pediatric Adverse Events Version 1.0, December, 2004 (Clarification dated August 2009)

**Female Genital Grading Table for Use in Microbicide Studies Addendum 1 to the Division of AIDS (DAIDS) Table for Grading Adult and Pediatric Adverse Events, Version 1.0, December 2004 (Clarification dated August 2009)

5.4 Co-enrollment Guidelines

As indicated in Section 5.2, participants must not take part in other research studies involving drugs, medical devices, vaginal products, or vaccines, after the Screening Visit and while taking part in MTN-024/IPM 031 unless approved by the Protocol Safety Review Team (PSRT) and Protocol Chair. Participation in the following types of studies may be allowed at the discretion of the IoR/designee after consultation with the Protocol Chair and PSRT:

- Participants may take part in MTN ancillary studies
- Participants who become infected with HIV may take part in observational and/or interventional studies for HIV-positive persons
- Participants who become pregnant may take part in observational studies, including pregnancy registries

Should any participant report concurrent participation in contraindicated studies after enrolling in MTN-024/IPM 031, the IoR/designee will consult the PSRT regarding ongoing product use and other potential safety considerations associated with co-enrollment.

6 STUDY PRODUCT

6.1 Regimen

Each participant will be randomized to one of two study regimens:

Table 2: Study Regimen

Group	N	Group Description
A	72	Dapivirine VR, containing 25 mg dapivirine
B	24	Placebo VR

Each participant will receive either a VR containing 25 mg dapivirine or a placebo VR. Participants will be randomized in a 3:1 ratio. The VR should be worn for approximately 28 consecutive days at a time but not more than 35 days before being replaced. A new VR will be inserted into the vagina at the Enrollment Visit and at each subsequent monthly visit. The previously inserted ring will be removed by the participant or clinician/designee at each monthly visit. The participant will be followed for approximately 1 week following the final VR removal.

6.2 Administration

The participant will self-insert (or insertion may be performed by clinician/designee, if necessary), the study VR at the Enrollment Visit and each subsequent visit when a VR is dispensed.

Study participants will be given detailed instructions in the clinic on proper VR insertion and removal procedures at the Enrollment Visit and at subsequent follow-up visits. The attempt of these procedures must be documented. Additional details on administration (ring insertion, removal, procedures in the event of expulsion or loss, including cleaning procedures) will be provided in the MTN-024/IPM 031 Study Specific Procedures (SSP) Manual.

6.3 Study Product Formulation

The study VR is an off-white, flexible ring containing either 25 mg of dapivirine or no drug (placebo) dispersed in a platinum-catalyzed-cured silicone matrix. The ring dimensions are as follows: 56 mm and 7.7 mm, outer diameter and cross-sectional diameter, respectively. The ring is designed to provide sustained release of drug over a 28-day period.

6.3.1 Dapivirine VR

Dapivirine 0.3125% (w/w) is dispersed in a flexible, opaque, cured silicone VR delivery device. The VR will contain 25 mg of dapivirine. The dapivirine VR should be stored at 15°C to 30°C.

6.3.2 Placebo VR

The placebo VR is manufactured with the same components as the drug-containing rings, except that it contains USP titanium dioxide dispersed in the silicone fluid as colorant, and no active pharmaceutical ingredient. The purpose of the colorant is for maintaining blinded conditions. The placebo VR should be stored at 15°C to 30°C.

6.4 Supply and Accountability

6.4.1 Supply

IPM ([name]) will oversee the manufacture of all of the study VRs and analysis/release of the rings under Good Manufacturing Practices (GMP).

6.4.2 Study Product Dispensing

Study VRs will be dispensed only to enrolled study participants or clinic staff on behalf of the participant, upon receipt of a written prescription from an authorized prescriber. Dispensing will take place on the day of enrollment and at each scheduled follow-up visit, except at the Final Clinic Visit.

6.4.3 Accountability

Each Clinical Research Site (CRS) Pharmacist of Record (PoR) is required to maintain a complete record of all study product received. The procedures to be followed are provided in the MTN-024/IPM 031 Pharmacist Study Product Management Procedures Manual.

All study product dispensed to a participant must be documented by the clinic staff when it is returned. This includes a ring that is brought back to the clinic by the participant and any ring removed at the clinic visit. Any study products not returned must also be documented by the clinic.

6.4.4 Retrieval of Study Product

Study product use for a participant may be temporarily held or permanently discontinued. Study product must be retrieved (optimally within 24 hours) and returned to the clinic when product use is permanently discontinued for HIV seroconversion (see table below). Additional study product retrieval specifications in response to product holds, discontinuations for other reasons, or IoR instruction, can be found in Table 3. Study product retrieval may occur either by the participant returning the VR (used) to study staff within the specified timeframe or attempts should be made by study staff to contact the participant and retrieve the study product as soon as possible.

Table 3: Retrieval of Study Product

	Retrieve Study Product
Permanent discontinuation or temporary hold due to potential HIV seroconversion	Within 24 hours
Permanent discontinuation for any other reason or IoR discretion	Within 5 working days
Temporary hold for reasons with expected duration of at least 7 days	Within 7 working days

In addition to the specifications listed above, under any circumstances, if product hold extends for 7 days or more, and product has not been retrieved as of the seventh day, study staff members must make every effort to retrieve study product within 7 additional working days.

It is not necessary to retrieve study products from participants for whom study product use is being temporarily held for less than 7 days. However, study products may be retrieved from such participants, to protect their safety, if there is concern that the participant may not comply with clinic staff instructions to refrain from study product use for the duration of the temporary hold. For all study product holds requiring retrieval of study product(s), if the study product(s) are not retrieved within timeframe stated in Table 3 above, the MTN-024/IPM 031 PSRT must be informed.

If prolonged use (greater than 35 days) of the study VR has occurred, attempts should be made to contact the participant and retrieve the study product as soon as possible.

For each participant, all VRs remaining in the participant's possession should be retrieved at the Final Clinic Visit. If the participant does not bring her remaining study product to this visit, study staff must arrange to retrieve the VR within 2 business days. If the study product(s) are not retrieved within that timeframe, the MTN-024/IPM 031 PSRT must be informed.

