9.3 General Criteria for Temporary Hold and/or Permanent Discontinuation of Study Product

A participant will be permanently discontinued from VR product use by the IoR/designee for any of the following reasons:

- The study VR should be held beginning immediately upon recognition of the first reactive HIV test. If via the algorithm in Appendix II the participant is determined to be HIV-uninfected, she may resume product use. The IoR/designee must permanently discontinue the study VR if HIV-1 infection is confirmed. See Section 9.7 for additional details regarding study termination. (permanent discontinuation)
- Allergic reaction to the VR. (permanent discontinuation)
- Pregnancy. (permanent discontinuation) See Section 9.8 for additional details regarding study termination.
- Reported use of PEP for HIV exposure. (permanent discontinuation)
- Reported use of PrEP for HIV prevention. (permanent discontinuation)
- Reported use of topical or systemic hormone replacement therapy requires a consultation with the PSRT regarding the need to temporarily hold study product. If a hold is required, the PSRT must be consulted prior to resuming study product use
- Participant is unable or unwilling to comply with required study procedures, or otherwise might be put at undue risk to their safety and well-being by continuing product use, according to the judgment of the IoR/designee.
 - The IoR/designee must consult the PSRT on all temporary product holds for this reason for further guidance on resuming product use, continuing the temporary hold, or progressing to permanent discontinuation.
 - If product use is temporarily held/permanently discontinued for this reason, but the underlying reason for the temporary hold later resolves, the IoR/designee must consult the PSRT to resume product use at that time.

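### Section 6.4.4 gives two different retrieval rules for a temporary hold of under 7 days for possible HIV seroconversion

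*Protocol*

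**What the plan says.** Four statements in the Protocol bear on this case.

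- **Section 9.3** starts the hold: "The study VR should be held beginning immediately upon recognition of the first reactive HIV test". If the Appendix II algorithm then shows the woman to be uninfected, she may go back to using the ring. If infection is confirmed, product is stopped for good.
- **Section 6.4.4, opening paragraph:** "Study product must be retrieved (optimally within 24 hours) and returned to the clinic when product use is permanently discontinued for HIV seroconversion". The paragraph then sends the reader to Table 3 for further retrieval rules, including those for product holds.
- **Section 6.4.4, Table 3, first row:** "Permanent discontinuation or temporary hold due to potential HIV seroconversion", with a limit of 24 hours. No length of hold is attached. The third row covers temporary holds expected to last at least 7 days and allows 7 working days.
- **Section 6.4.4, below Table 3:** "It is not necessary to retrieve study products from participants for whom study product use is being temporarily held for less than 7 days". The next sentence makes retrieval optional: "However, study products may be retrieved from such participants, to protect their safety, if there is concern that the participant may not comply" with instructions not to use the product.

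The same paragraph ends with the duty to inform the PSRT. That duty is limited to holds for which retrieval is required and the Table 3 time limit has been missed.

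**The concern.** A short hold for possible seroconversion meets the description in the first row of Table 3 and also the description in the under-7-day sentence. One asks for the ring back within 24 hours. The other asks for nothing unless staff doubt that the woman will comply. A site could follow one statement and breach the other within the same section, and two sites could handle the same event differently while each believed it was compliant.

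This is a participant-safety rule. Retrieval guards against a ring being used despite the hold, and the active ring contains a single NNRTI. Reporting is affected too: whether the PSRT must be told of an unretrieved ring depends on whether retrieval was required in the first place.

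**Working it through.** No sample size, rate or test is involved, so there is no figure to reproduce. The check compares the scope of each rule and then traces one case through them.

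**Scope of the two statements in section 6.4.4**

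| | Table 3, first row | Under-7-day sentence |
|---|---|---|
| Reason for hold | Possible HIV seroconversion | Any; none excepted |
| Length of hold | Any; no minimum | Less than 7 days |
| Retrieval | Required, 24 hours | Not necessary; optional if compliance is doubted |
| PSRT told if ring not retrieved | Yes, once 24 hours pass | Not triggered, since retrieval was not required |

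The overlap is a hold for possible seroconversion that lasts under 7 days. The instructions differ there, and neither section 6.4.4 nor section 9.3 states an order of precedence.

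**Is the overlap a foreseen case?** Yes. Section 9.3 makes the HIV hold temporary and reversible. How often it ends within 7 days cannot be read from the document, because the Appendix II figure is not shown.

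**Where it can arise.** HIV serology is required in follow-up only at week 12 (Table 7, Appendix I). At that visit the ring is collected and no new one is dispensed. At weeks 4 and 8 serology is done only if indicated, and a new ring is inserted (Table 6). The case therefore needs a reactive test done for cause at week 4 or 8, or at an interim visit, in a woman who has a ring.

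**What the two statements lead to**

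1. *Algorithm negative, hold under 7 days.* Table 3 has the ring back within 24 hours. Under the later sentence it is never retrieved, and use may resume.
2. *Infection confirmed in under 7 days.* The hold becomes a permanent discontinuation, for which Table 3 sets 24 hours on any reading. A site that had relied on the later sentence would then retrieve the ring less than 7 + 1 = 8 days after the hold began, against 1 day under the first row. The difference is a delay, not a missing retrieval.
3. *Hold of 7 days or more.* The under-7-day sentence no longer applies and the conflict disappears. At hour 24, however, the site may not yet know which kind of hold it has.

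**The case against.** The strongest reply is that section 6.4.4 has an ordinary reading without conflict. The first row of Table 3 names a specific reason and expressly includes temporary holds. The third row covers holds expected to last at least 7 days, and the under-7-day sentence is simply its complement: other holds, too short for that row. This reading is reasonable. The Protocol does not state it, however. The paragraph before the short-hold sentence says that it adds to the rules above it; the short-hold sentence carries no such wording and no exception for HIV. Staff at several sites would have to infer the precedence.

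Other parts of the reply succeed and limit the point:

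- A reader might count the opening paragraph as a third conflicting rule, because it ties mandatory retrieval to permanent discontinuation. It does not say that retrieval is confined to that case, and it refers holds to Table 3.
- A reader might infer that the PSRT would hear nothing. The introduction to section 9 generally calls for immediate PSRT consultation on holds unless otherwise specified, and requires all holds to be recorded on case report forms. Section 6.4.3 requires unreturned product to be documented. What depends on the reading is the specific duty in section 6.4.4 to report an unretrieved ring.
- A reader might cite the resistance data in section 2.4.1 as a demonstrated hazard. Those data concern prolonged exposure in culture, around 30 days, and the Protocol says their clinical relevance is not known. They do not describe a ring held for under 7 days.
- A reader might suppose that every reactive screening result is affected. Women who are reactive at the Screening Visit have no ring.

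**Conclusion.** The inconsistency stands in a narrow form. For a temporary hold of under 7 days for possible HIV seroconversion, section 6.4.4 both requires retrieval within 24 hours and says retrieval is not necessary, and the section's PSRT notice for an unretrieved ring follows whichever statement is applied.

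The documents do not support reading this as permission for a possibly infected woman to keep using the ring. Section 9.3 stops use at the first reactive test, and confirmed infection brings the 24-hour rule into force on any reading. The matter is possession of a held ring.

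The number affected cannot be calculated but should be small: about 96 women followed for about 13 weeks, with routine follow-up serology only at the visit where rings are collected. With 3:1 allocation about one ring in four would be placebo, although blinded staff could not tell which.

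The conclusion assumes that some HIV holds end within 7 days. If the algorithm always took longer, the two statements would not collide for a completed hold. Because this is a safety instruction and the correction is cheap, it is worth making despite its rarity.

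**What to change.** Reconcile the under-7-day sentence in section 6.4.4 with the first row of Table 3 by stating whether that sentence covers holds for possible HIV seroconversion. Tie the PSRT notification for unretrieved product to the reconciled rule, so that the reporting duty no longer depends on how a site reads the section. Which retrieval rule should apply is a clinical decision for the protocol team.

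The cost is one or two sentences of protocol wording, carried through to the study-specific procedures manual. Data collection, sample size and analysis do not change.
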